8.2.6 Other Safety Data

8.2.6.1 Special Pediatric Safety Assessments

A data summary will be provided for the 24-month open-label treatment period only, since in the conversion period there are no special pediatric safety assessments such as the NY-AACENT and UKU Side Effects Rating Scale assessment.

The NY-AACENT will be performed at the baseline visit, all protocol-specified scheduled visits, and at the early termination (ET) visit. The incidence of sign/symptom items as recorded in the NY-AACENT scale will be summarized. Specifically, the incidence (and severity) of the sign/symptom items will be tabulated by trial visit, based on the OC data. The summarization will be repeated for the subset of *drug-related* signs or symptoms and for the subset of *function-impaired* signs or symptoms, respectively. Additionally, change from baseline in the NY-AACENT total score will be summarized on the OC data by trial visit and on the LOCF data for the last assessment visit.

See [Section 8.2.7](#) for the construction of the NY-AACENT total score.

The UKU Side Effects Rating Scale assessments will be administered at the baseline visit, all protocol-specified scheduled visits, and at the ET visit. The incidence (and severity) of the individual side effects and categories of side effects as recorded in the UKU Side Effects Rating Scale will be tabulated by trial visit, based on the OC data. The summarization will be repeated respectively for the subset of having “improbable”, “possible”, and “probably” connection to the IMP. In addition, a by-visit summarization will be provided for the following assessments: (i) the global assessment of the interference by existing side effects with the subject’s daily performance, and (ii) the consequence (ie, the measures taken with respect to the side effects).

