8.2.6.2 Extrapiramidal Symptoms

A data summary will be provided for the 24-month open-label treatment period only, since there are no assessments of the EPS scales in the conversion period.

Three EPS scales including the SAS, AIMS, and BARS will be assessed at the baseline visit and the following visits in the 24-month open-label treatment period: Weeks 1, 2, and 4; Months 2, 3, 4, 6, 8, 10, 12, 15, 18, and 24; or an ET visit. Change from baseline in each of the 3 EPS variables (SAS total score, AIMS total score, and BARS global clinical assessment score) will be summarized on the OC data by visit and on the LOCF data for the last assessment visit. In addition, the BARS global clinical assessment will be treated as a categorical variable taking values (categories) of “Absent”, “Questionable”,

“Mild Akathisia”, “Marked Akathisia”, and “Severe Akathisia”, and thus will be summarized on OC data by visit for each severity category, by using count and frequency.

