8.2.6.3 Suicidality

Suicidality will be monitored during the trial (including the 1- to 4-week conversion period but excluding the 21-day follow-up period) by using the C-SSRS. A data summary will be provided separately for the open-label treatment period and for the conversion period.

Suicidality data (including suicidal ideation, suicidal behavior) will be collected at all scheduled visits and the ET visit.

Suicidal ideation has 5 types or levels, with increasing severity from “wish to be dead” to “active suicidal ideation with specific plan and intent”. The incidence of each type of suicidal ideation will be summarized for the reporting period (ie, separately for the open-label period and for the conversion period). Suicidal behavior has several types or levels ranging from “actual attempt”, “interrupted attempt”, “aborted attempt” to “completed suicide”. The incidence of each type of suicidal behavior will be summarized for the reporting period.

Additionally, the incidence of each of the following 4 categories of treatment-emergent suicidality will be summarized for the reporting period: (1) Emergence of suicidal ideation, which is defined as having an occurrence of any suicidal ideation during the reporting period while having no suicidal ideation at the baseline (relative to the reporting period); (2) Emergence of serious suicidal ideation, which is defined as having an observation of suicidal ideation severity rating of 4 or 5 during the reporting period while having no suicidal ideation at the baseline (relative to the reporting period); (3) Worsening of suicidal ideation, which is defined as having had a suicidal ideation severity rating that is more severe compared to the baseline (relative to the reporting period); and (4) Emergence of suicidal behavior, which is defined as reporting of any suicidal behavior during the reporting period while there was no suicidal behavior at the baseline (relative to the reporting period). Specifically, for each category of treatment-emergent suicidality as defined above, the number and percentage of subjects having experienced the event of interest during the reporting period will be tabulated.

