8.2.6.4 Tanner Stage

A data summary will be provided for the 24-month open-label treatment period only. There are no ratings of the Tanner Staging (a classification of sexual maturity stages) in the conversion period.

The Tanner Staging scores are collected at baseline and at the following scheduled visits in the 24-month open-label treatment period: Months 6, 12, 18, and 24. The shifting frequency in Tanner Staging score (an ordinal score of 1 to 5) between baseline and each postbaseline visit will be tabulated separately for boys and girls by using cross-frequency. If the subject is rated “5” at a visit before Month 24 and is not rated thereafter, missing ratings at the subject’s subsequent visits will be imputed with the value of “5”.

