10.5 Data Imputation for the Last Assessment Visit

A landmark time point for the trial is the end-of-trial visit (the Month 24 visit) in the open-label treatment period of the trial. For some reason, a subject may be discontinued early from treatment before the end-of-trial visit. Such a subject will be invited to an ET visit where the assessments originally scheduled for the Month 24 visit will be collected.

It is anticipated that there will be many ongoing subjects at the time of the interim analysis database lock. For purposes of the interim data reporting, the LOCF rule will be applied to all subjects (including all ongoing subjects) in deriving the last visit's value for the subjects. If this trial is completed to the extent that the last enrolled subject has had an

opportunity to complete 24 months' open-label treatment, then the value at the 24-month visit or at the ET visit will be taken as the value for the last visit.

In deriving the last visit data, the LOCF rule will be applied to the following parameters: PANSS (including Total Score, Positive subscale score, Negative subscale score), CGI, SAS, AIMS, BARS, body weight, waist circumference, height, BMI, vital signs, ECG, clinical laboratory tests, CGAS, NY-AACENT, UKU Side Effects Rating Scale, Tanner Staging, and pregnancy tests. The LOCF rule will also be applicable to the individual PANSS items in deriving the last visit data. Note that only the postbaseline data can be carried forward in deriving the last visit data.

In general, the by-visit analysis (eg, summary) of a variable will also include the analysis for the derived last visit.

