10.6 Descriptive Statistics for Continuous and Categorical Variables

For continuous variables, descriptive statistics include N (ie, number of subjects with non-missing value), mean, SD, median (Med), quartile, minimum (Min), and maximum (Max). For categorical (eg, nominal or dichotomous) variables, descriptive statistics refer to frequency distribution (eg, count and percentage).

In general, ordinal variables with fewer categories (say, ≤ 4) will be handled as categorical variables, whereas ordinal variables of ≥ 5 categories (such as assessment scores on many of the scales used in this trial) will be treated as continuous.

Unless specified otherwise, the denominator used for calculating percentage will be the number of unique subjects (or say, the number of subjects "at risk") in the analysis sample (or its subgroup of interest). And whenever applicable, a row of "Missing/Unknown" will be presented along with rows of recorded outcomes for the tabulation of the categorical variables.

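### UKU side-effect items are tabulated by visit with no subject-level comparison with baseline, so new or worsened symptoms cannot be told apart from pre-existing ones

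*SAP*

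**What the plan says.** Protocol 3.5.2.1 lists both UKU and NY-AACENT as secondary safety endpoints. Under protocol Tables 3.7-1 and 3.7-2 they are rated at baseline and at 14 scheduled visits afterwards: Weeks 1, 2 and 4, and Months 2, 3, 4, 6, 8, 10, 12, 15, 18, 21 and 24.

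**UKU.** SAP 8.2.6.1 gives the incidence and severity of individual side effects and categories "as recorded in the UKU Side Effects Rating Scale will be tabulated by trial visit, based on the OC data". These tables are repeated by the rater's view of the connection to study drug. Global interference and consequence are also summarised by visit. SAP 8.2.7 codes each item 0 to 3 and defines no total, change or shift variable.

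**NY-AACENT.** SAP 8.2.6.1 treats items the same way: "the incidence (and severity) of the sign/symptom items will be tabulated by trial visit, based on the OC data". For this scale there is also a baseline comparison, but of the total only: "change from baseline in the NY-AACENT total score will be summarized on the OC data by trial visit and on the LOCF data".

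**Last visit.** SAP 10.5 puts both scales on its LOCF list and states: "In general, the by-visit analysis (eg, summary) of a variable will also include the analysis for the derived last visit".

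**The other rating scales in SAP 8.2.**
- SAS, AIMS and BARS have change from baseline (8.2.6.2).
- Tanner stage has a shift table: "The shifting frequency in Tanner Staging score (an ordinal score of 1 to 5) between baseline and each postbaseline visit" is tabulated (8.2.6.4).
- C-SSRS has emergence categories and one for worsening: "Worsening of suicidal ideation, which is defined as having had a suicidal ideation severity rating that is more severe compared to the baseline" (8.2.6.3).

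**The concern.** The SAP uses the word incidence, but a count made visit by visit without regard to baseline status is the percentage of subjects with the symptom present. It mixes symptoms carried in at entry with symptoms that appeared or got worse on open-label treatment.

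That matters here because the trial has one arm, so a subject's own baseline is the main reference. Pre-existing symptoms are to be expected. The protocol Introduction describes greater cognitive impairment in early-onset illness, and SAP 7.1.1 sets the rollover baseline at Week 6 of the parent trial, after treatment there. Illness symptoms that resolve can offset new side effects, leaving the by-visit percentage flat. What is at stake is whether the report can say how many adolescents newly developed or worsened in a given UKU symptom.

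**Working it through.** The documents state no figure on this point, so there is nothing to reproduce. The rates below are assumptions chosen for illustration. Only the visit count (14) and the number of NY-AACENT items (7, SAP 8.2.7) come from the documents.

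**1. What two by-visit percentages reveal.** Let b be the proportion with an item present at baseline and v the proportion at a visit, in the same subjects. The proportion present at the visit but absent at baseline lies between max(0, v − b) and min(v, 1 − b).

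| b | v | Newly affected at the visit |
|---|---|---|
| 0.30 | 0.29 | 0 to 0.29 |
| 0.20 | 0.20 | 0 to 0.20 |
| 0.10 | 0.15 | 0.05 to 0.15 |

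One case inside the first row: half of the 30% resolve (0.30 × 0.5 = 0.15) and 20% of the other 70% are new (0.70 × 0.20 = 0.14). Prevalence is 0.30 − 0.15 + 0.14 = 0.29. The table shows a one-point fall while 14% are new cases. Because the tables use observed cases, the subjects contributing also change over time, which adds further ambiguity.

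**2. NY-AACENT, where the total has change from baseline.** Suppose each of the 7 items moves up one degree with probability 0.14, down one with 0.15, and otherwise stays. The mean change in total is 7 × (0.14 − 0.15) = −0.07.
- Independent items: SD = √(7 × (0.29 − 0.0001)) = 1.42, so the spread would be visible in the SAP 10.6 statistics. P(at least one item worse) = 1 − 0.86⁷ = 0.652. P(total worse), summed over the trinomial outcomes with more items up than down, is 0.339. The difference, 0.652 − 0.339 = 0.313, is the share with a worse item behind an unchanged or better total.
- Perfectly correlated items: SD = 7 × √(0.29 − 0.0001) = 3.77. P(item worse) = P(total worse) = 0.14, so nothing is hidden.

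The item-level loss for NY-AACENT thus runs from 0% to 31% in this example, depending on correlation. UKU has no total to fall back on.

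**3. Why a simple worst-value count is not the answer.** If chance alone produced a raised rating independently at 3% per visit, the share ever raised would be 1 − 0.97⁷ = 0.19 by Month 6 (7 visits), 1 − 0.97¹⁰ = 0.26 by Month 12 (10 visits) and 1 − 0.97¹⁴ = 0.35 by Month 24. Restricted to degree 2 or more, at an assumed 0.5% to 1% per visit, it would be 1 − 0.995¹⁴ = 0.068 to 1 − 0.99¹⁴ = 0.131. There is no control arm from which to estimate this noise.

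**The case against.** The strongest reply is that the SAP already does what was promised. Protocol 3.5.2.1 and 7.5.5.1 ask for item frequencies, plus a possible NY-AACENT total and its change. SAP 8.2.6.1 gives these and adds severity, attribution and impairment subsets. That stands: a reader might infer that a protocol-specified endpoint has been left unanalysed, and the documents do not support that.

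A reader might also infer that NY-AACENT is neglected in the same way as UKU. It is not. It has total-score change and item frequencies, so it is handled at least as fully as SAS and AIMS, which have total-score change only. Nor do the other rating scales all have whole-period worsening counts; only C-SSRS does.

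The adverse event tables are a further channel. SAP 8.1.1 counts new events and baseline events that intensify, somnolence and extrapyramidal symptoms are separate topics in SAP 8.1, and adverse events are also collected at the remote monthly contacts. A reader might therefore go too far in saying that emergence is not captured at all. The cover is still partial. Protocol 5.2 elicits events with one open question and generally keeps illness exacerbation out. The available text contains no rule turning a UKU rating into an adverse event, although the scale forms (protocol Appendices 12 and 13) are not included in it, so such a rule cannot be excluded. The UKU drug-connection subsets are rater opinion and are also by visit. Listings (SAP 10.7) would allow a later derivation, but one not specified in advance.

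Finally, no document figure shows how large the loss would be in practice. That is true, and it limits the weight of the point.

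**Conclusion.** The point holds for UKU. It is the one rating scale in SAP 8.2 with no within-subject comparison with baseline, so the planned tables cannot say how many subjects newly developed or worsened in a UKU symptom. For NY-AACENT it is a secondary matter, confined to items.

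The bounds in the working follow from the table layout and do not depend on the assumed rates; where the truth lies within them is unknown. No sample size, error rate or stated figure is affected, and the trial plans no inferential analysis. The by-visit tables are correct for what they show. This is a cheap and worthwhile improvement to a descriptive secondary safety analysis, not an error or a departure from the protocol.

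**What to change.** In SAP 8.2.6.1, keep the by-visit tables and add the following.

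- For each UKU item, a shift table of open-label baseline degree (0 to 3) against the degree at each visit and at the last visit. The same for NY-AACENT items (0 to 4) is optional.
- From each table, the number and percentage of subjects with a degree above baseline, and with worsening to degree 2 or more. The denominator is subjects with a baseline rating and a rating at that visit (for the last visit, any post-baseline rating). Use the SAP 10.7 columns.
- If a whole-period count is wanted, restrict it to worsening to degree 2 or more and read it beside exposure and the by-visit tables.
- No shift rows for UKU categories, because SAP 8.2.7 defines degrees for items only.
- A footnote that, for rollovers from brexpiprazole and de novo subjects who went through conversion, these counts show further worsening after entry, not first onset on the drug.

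The cost is SAP wording and added output from data already collected. Two limits remain: some rating noise with no control arm to subtract it, and drug effects already present at baseline are not counted. NY-AACENT, by the protocol's own statement, is not validated, which is a further reason to keep its item shifts optional.

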8.2.6.2 Extrapiramidal Symptoms

A data summary will be provided for the 24-month open-label treatment period only, since there are no assessments of the EPS scales in the conversion period.

Three EPS scales including the SAS, AIMS, and BARS will be assessed at the baseline visit and the following visits in the 24-month open-label treatment period: Weeks 1, 2, and 4; Months 2, 3, 4, 6, 8, 10, 12, 15, 18, and 24; or an ET visit. Change from baseline in each of the 3 EPS variables (SAS total score, AIMS total score, and BARS global clinical assessment score) will be summarized on the OC data by visit and on the LOCF data for the last assessment visit. In addition, the BARS global clinical assessment will be treated as a categorical variable taking values (categories) of “Absent”, “Questionable”,

“Mild Akathisia”, “Marked Akathisia”, and “Severe Akathisia”, and thus will be summarized on OC data by visit for each severity category, by using count and frequency.

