### **3.7.3.5.2      Abnormal Involuntary Movement Scale**

The AIMS assessment ([Appendix 10](#)) consists of 10 items describing symptoms of dyskinesia. Facial and oral movements (items 1 through 4), extremity movements (items 5 and 6), and trunk movements (item 7) will be observed unobtrusively while the subject is at rest (eg, in the waiting room), and the investigator will also make global judgments on the subject's dyskinesias (items 8 through 10). Each item will be rated on a 5-point scale, with a score of zero representing absence of symptoms (for item 10, no awareness), and a score of 4 indicating a severe condition (for item 10, awareness, severe distress). For this scale, the subject is to be sitting on a hard, firm chair. In addition, the AIMS includes two yes/no questions that address the subject's dental status. Anticholinergics, propranolol, benzodiazepines, and non-benzodiazepine sleep aids are not permitted within 12 hours of scale administration (see [Section 4](#)). Investigators are encouraged to delay scale administration until 12 hours have elapsed, if at all possible. However, if delaying administration of the scale is not feasible, the AIMS should still be administered and the use of the medication documented, including a notation of the drug name, dose, and time of administration on the eSource.

The AIMS Movement Rating Score is defined as the sum of items 1 through 7 (ie, items 1 through 4, facial and oral movements; items 5 and 6, extremity movements; and item 7, trunk movements).

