## 4.2 Other Restrictions

### 4.2.1 Restricted Therapies and Precautions

Any history of electroconvulsive therapy is exclusionary.

Use of intramuscular (IM) benzodiazepines is prohibited throughout the trial. Short-term use of specific oral benzodiazepines is allowed during the trial for the control of agitation or insomnia as shown in [Table 4.1-3](#). Short-acting benzodiazepines (ie, lorazepam or oxazepam) are to be used whenever possible. In countries or institutions where no short-acting benzodiazepines are commercially available, use of oral diazepam or oral clonazepam may be acceptable if prior authorization is obtained from the medical monitor. The investigator should contact the medical monitor to discuss any subject who requires frequent use of a benzodiazepine for agitation or insomnia beyond the first 2 weeks of the trial.

Non-benzodiazepine sleep aids (ie, zolpidem, zaleplon, zopiclone, and eszopiclone only) are permitted for the treatment of insomnia, but not on the same day as administration of a benzodiazepine, regardless of indication. For the non-benzodiazepine sleep aids, sites should only utilize 1 of the listed medications that are approved for this indication in their respective countries and the country-specific prescribing information is to be used to determine the maximum allowable daily dose for the treatment of insomnia.

Anticholinergics are permitted for the treatment of EPS up to a maximum of 4 mg/day benztrapine or its equivalent and propranolol is permitted for akathisia or tremor up to a maximum of 60 mg/day. Subjects receiving a stable dose of propranolol for other conditions at entry into Trial 331-10-236 may remain on propranolol. Trial sites should only utilize medications that are approved for these indications in their respective countries.

Benzodiazepines, non-benzodiazepine sleep aids, anticholinergics, and propranolol must not be administered within 12 hours prior to scheduled efficacy and safety assessments, including EPS scales. Investigators are encouraged to delay scale administration until 12 hours have elapsed, if at all possible. However, if delaying administration of efficacy and safety scales is not feasible, the scales should still be administered and the use of the medication documented, including a notation of the drug name, dose, and time of administration on the eSource.

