#### **7.5.5.2      Extrapyramidal Symptoms**

Descriptive statistics will be provided for the mean change from baseline to end of period in SAS, AIMS, and BARS scores for the Safety Sample. Results will be summarized by visit.

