8.2.7 Computational Details for Safety Scales

- 1) The SAS total score is the sum of rating scores over 10 items from the SAS panel in the eSource. The SAS total score is treated as unevaluable if fewer than 8 of the 10 items are recorded. If 8 or 9 of the 10 items are recorded, the SAS total score will be calculated as the mean of the recorded items multiplied by 10 and then rounded to the first decimal place.
- 2) The AIMS movement total score is the sum of rating scores for facial and oral movements (ie, items 1 - 4), extremity movements (ie, items 5 - 6), and trunk movements (ie, item 7). The AIMS total score will be treated as unevaluable if fewer than 6 of the 7 items are recorded. If 6 of the 7 items are recorded, the total score will be calculated as the mean of the recorded items multiplied by 7 and then rounded to the first decimal place.
- 3) The BARS score is based only on the item of “Global Clinical Assessment of Akathisia”. The BARS consists of 4 items related to akathisia as follows. Item 1: objective observation of akathisia by the investigator; Item 2: subjective feelings of restlessness by the subject; Item 3: subjective distress due to akathisia; and Item 4: global clinical assessment of akathisia. The first 3 items will be rated on a 4-point Likert scale from 0 to 3, with 0 representing the absence of symptoms and 3 representing a severe condition. The BARS global clinical assessment score refers to the ratings from the fourth item Global Clinical Assessment of Akathisia, which is a 6-point Likert scale from 0 to 5, with 0 representing absence of symptoms and 5 representing severe akathisia. Thus, the BARS global clinical assessment score ranges from 0 to 5.

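### The SAS and AIMS have no incidence, shift or worst-value summary, and AIMS items 8 to 10 are not analysed, so the number of adolescents whose ratings worsened cannot be read from the scale tables

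*SAP*

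**What the plan says.** Protocol 7.5.5.2 sets the analysis: "Descriptive statistics will be provided for the mean change from baseline to end of period in SAS, AIMS, and BARS scores". SAP 8.2.6.2 carries it out as "Change from baseline in each of the 3 EPS variables (SAS total score, AIMS total score, and BARS global clinical assessment score", by visit on observed cases and at the last visit by LOCF. Under SAP 10.6 each such summary gives N, mean, SD, median, quartiles, minimum and maximum.

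Only one scale gets more: "the BARS global clinical assessment will be treated as a categorical variable", with counts at each visit.

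The AIMS score analysed covers items 1 to 7. SAP 8.2.7 opens with "The AIMS movement total score is the sum of rating scores for facial and oral movements (ie, items 1 - 4" and goes on to add items 5 to 7. The form holds more than that: protocol 3.7.3.5.2 says "the investigator will also make global judgments on the subject's dyskinesias (items 8 through 10". Those three items appear in no SAP summary.

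SAP 10.2 assigns EPS ratings to analysis windows. When several fall in one window, only the last enters the by-visit tables; all of them go to the listing.

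**The concern.** The trial's objective is long-term safety over 24 months in adolescents. For movement disorder the basic question is how many subjects got worse on examination. A change-from-baseline summary of a total does not answer it, because a few worsened subjects are averaged with many unchanged ones.

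The SAP does count subjects for its other safety measures: laboratory shifts (8.2.1), weight change of at least 7% (8.2.3.1), vital-sign and ECG abnormalities (8.2.4.1, 8.2.5), emergent suicidality (8.2.6.3) and Tanner shifts (8.2.6.4). Dyskinesia and parkinsonism ratings are left out of that practice, although the data are collected. The report could state a mean AIMS change near zero and give no count beside it.

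**Working it through.** **Inputs from the documents.** The SAS has 10 items scored 0 to 4, so its total runs from 0 to 10 × 4 = 40 (protocol 3.7.3.5.1). The AIMS total uses 7 items scored 0 to 4, so it runs from 0 to 7 × 4 = 28. SAP section 4 anticipates about 350 subjects, then says fewer are expected because the parent trial was cut to 315, and hopes for at least 100 with 12 months of exposure. Neither document gives a score distribution, so the number affected (k) and the rise (d) below are assumptions. There is no planned figure to reproduce.

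**Dilution.** With k subjects rising d points and the rest unchanged, mean change = k × d / N.

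| N | k = 3, d = 4 | k = 5, d = 6 | k = 10, d = 8 |
|---|---|---|---|
| 350 | 0.03 | 0.09 | 0.23 |
| 315 (illustrative) | 0.04 | 0.10 | 0.25 |
| 100 | 0.12 | 0.30 | 0.80 |

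The median and both quartiles are 0 in every cell. At N = 350 the SDs are 0.37, 0.71 and 1.33, and the maxima are 4, 6 and 8.

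**Can the number affected be recovered from the planned statistics?** Take N = 200 (assumed) and two data sets:
- A: 10 subjects at +4, 190 at 0. Mean = 40/200 = 0.20. SD = √[(10 × 16 − 200 × 0.20²)/199] = √(152/199) = 0.87.
- B: 1 subject at +4, 36 at +1, 163 at 0. Mean = (4 + 36)/200 = 0.20. SD = √[(16 + 36 − 8)/199] = √(44/199) = 0.47.

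Both have minimum 0, quartiles 0, median 0 and maximum 4. One has ten subjects up by 4 points, the other has one. Only the SD differs, and it is not a count. Maxima at successive visits cannot be added up either, because the same subject may supply several of them.

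**Loss within windows.** The Month 12 window is days 329 to 412, which is 84 days. If an unscheduled AIMS is high on day 340 and the scheduled one on day 372 is lower, only the second enters the table. The LOCF last-visit summary does not recover the first. It survives in the listing alone.

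**The case against.** The case on the other side is substantial.

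- **The tables hold more than a mean.** SD, quartiles, minimum and maximum are reported by visit, and listings hold every rating. A reader might infer that affected adolescents would be invisible; the documents do not support that.
- **Other analyses count subjects.** SAP 8.1 tabulates EPS-related TEAEs, with and without akathisia. SAP 8.2.6.1 tabulates incidence and severity of each UKU side effect by visit, from a scheduled clinician rating made at the same visits. Although "Anticholinergics are permitted for the treatment of EPS up to a maximum of 4 mg/day", with propranolol also allowed, SAP 8.3 tabulates such use by drug class and generic name.
- **There is no contradiction.** The SAP implements the protocol's own endpoint on the protocol's own AIMS score, and the EPS scales are secondary endpoints. The BARS global is a single ordinal item, so category counts come naturally there. Akathisia (7.5%) is the one EPS term among the frequent TEAEs in protocol 1.3.

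All of this stands and limits the point, but it does not supply the missing count. AEs are elicited by a general, non-leading question (protocol 5.2), and two or more EPS symptoms are entered under the single term extrapyramidal syndrome (protocol 5.1), so the TEAE tables can lose the distinction between dyskinesia and parkinsonism. The UKU form is not in the text available for this review, so its motor items could not be checked, and its tables are by visit with no stated overall count of new cases.

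**Conclusion.** The point holds as a gap in a descriptive plan, worth closing because closing it is cheap. No planned scale table shows how many subjects worsened on the SAS or AIMS. Under the assumptions above, 3 to 10 affected subjects give a mean change of 0.03 to 0.25 at 315 to 350 subjects. Dilution weakens as numbers fall: at 100 observed the range is 0.12 to 0.80.

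Three stronger readings are tempting and are not supported:
- That the zero floor of the scales pulls the mean to zero. It does not; dilution by unchanged subjects does.
- That improvement in other subjects will cancel the signal. It is arithmetically possible (at N = 350, 5 × 6 − 15 × 2 = 0), but the documents give no score distribution to show that it is likely.
- That AIMS item 8 with a set threshold defines a case. Protocol 3.7.3.5.2 calls items 8 to 10 global judgments and identifies only item 10, as awareness. Neither document gives a cut-off for any item.

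**What to change.** Keep the mean-change tables. Add to SAP 8.2.6.2, for the overall open-label period and in the display columns of SAP 10.7, shift tables of baseline against worst post-baseline score (0 to 4) for:
- (a) each of AIMS items 8, 9 and 10;
- (b) the highest single score among AIMS items 1 to 7;
- (c) the highest single SAS item score.

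Use all post-baseline ratings, including early-termination and unscheduled ones, and give the number and percentage of subjects who worsened from baseline. State how missing items and missing baselines are handled, and whether the 7-day limit after last dose in the note to Table 10.2-1 applies. No cut-off is needed; if the sponsor wants one, it should justify it and fix it before database lock.

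The cost is SAP wording and a few more tables from data already collected. The downside is that worst-value counts rise with the number of visits, include transient ratings and have no concurrent control, so they should be read beside exposure. A highest-item score also misses mild spread across several items, which the retained mean-change tables still reflect.
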